4.6.3 Health economic outcomes

Costs of the installation of the software program and training of the general practice staff to use the software (**Outcome 10**) will be summarised using descriptive statistics.

Health care service costs (**Outcome 11**) will be compared between the intervention and control arms using a GLM with a log link and gamma distribution, two-part model or mixtures model depending on the distribution of costs.

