The FHT trial is a stratified head-to-head cluster randomised controlled trial. The unit of randomisation is the general practice, where practices are randomly allocated concurrently on 1:1 ratio to either participate in the FHT CKD QI module (intervention arm) or the FHT Cancer-risk module (active control arm for the CKD study). All general practices will be provided access to the respective QI programs at the commencement of the trial (October 4th, 2021). Please refer to the trial protocol for a detailed description of the intervention and comparator.

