3.1 Level of statistical significance and confidence intervals

Estimates of the intervention effect will be reported with 95% confidence intervals and two sided-p-values.

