(9) The rate of general practice encounters per patient over the trial period. This will be calculated using total number of general practice encounters in the 12-month trial period of all eligible patients with a diagnosis or pathology results consistent with CKD at baseline divided by the total time they were observed in the trial. For each patient, time will be one year, calculated from the date the trial commenced (4th October 2021) to the end of the trial (30th September 2022), except for patients/practices that discontinued during the trial period, where time observed will be calculated from the 4th October 2021 to the date the patient(s) discontinued/withdrew.

Health economics outcomes are:

(10) The cost of the installation for the software program for QI, training, QI support and education. This will be calculated at the general practice level, using cost data collected by Health and Biomedical Informatics Centre (HABIC R²) who developed and provided technical support for the FHT software and the FHT investigators and research team who liaised with practices and facilitated the education sessions.

(11) Cost of primary care service utilisation per patient per year. These will be calculated based on Medicare items, Provider Charge, Schedule Fee, Patient Out of Pocket in the Medicare Benefits Schedule (MBS) data linked to patients in the Patron for the FHT evaluation.

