4.6.1 Primary outcome

For the primary outcome, the odds ratio (relative measure) and the difference in proportions between the intervention and control arms (absolute measure) will be estimated using a generalised linear model (GLM) with the logit link and identity link functions, respectively, and binomial distribution for both models. Both models will include randomisation stratification factors, GP FTE and IRSD terciles as covariates, and use Generalised Estimating Equations with an exchangeable correlation structure and robust standard errors to allow for correlation of outcomes within general practice. If the model used to

estimate the risk difference fails to converge, the risk difference will be derived from the GLM with the logit link function.^{9,10}

Absolute (difference in proportions between the intervention and control arms), and relative (odds ratio) estimated intervention effects for the primary outcome will be reported with 95% confidence intervals and p-values.

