4.6.2 Secondary outcomes

Statistical methods described for the primary outcome will be used for the **binary secondary outcomes 1, 2, and 6.** For each outcome, an additional covariate will be fitted in the regression model. For outcome 1, we will adjust for whether a recommendation would have been made to consider initiating ACEIs or ARBs for the patient (yes/no). Similarly for outcome 2, we will adjust for whether the recommendation would have been received to consider initiating statins (yes/no). For outcome 6, we will include uACR at baseline as a covariate.

For the analysis of continuous secondary **outcomes 3, 4, 5 and 8**, a mixed effects linear model with study arm, baseline measure of the outcome (where appropriate), randomisation stratification factors (GP FTE and IRSD terciles) will be fitted as fixed effects and general practice as a random effect. The estimated intervention effects will be reported as the difference in means between the intervention and active control arms with 95% confidence intervals and p-values.

Outcomes with a skewed distribution may be log-transformed, in which case, the estimated intervention effect will be reported as a ratio of the geometric means between study arms, with their respective 95% confidence interval and p-value.

Secondary outcome 7 will be analysed using the proportional odds logistic regression model with randomisation stratification factors (GP FTE and IRSD terciles) and baseline CVD risk group included as fixed effects. Generalised Estimating Equations with an exchangeable correlation structure and robust standard errors will be used to allow for correlation of outcomes within general practice. An alternative model will be considered if the assumption of proportional odds is not met.¹¹

The estimated intervention effect will be reported as a cumulative odds ratio with their respective 95% confidence interval and p-value.

Secondary outcome 9 will utilise a Poisson mixed effects model (or a Negative Binomial mixed effects model if overdispersion is detected), with fixed effects for study arm and the randomisation stratification factors (GP FTE and IRSD terciles), and random effect for general practice. The estimated intervention effect will be reported as differences in rate between the intervention and control arms and rate ratios with 95% confidence intervals and p-values.

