4.4.6 Health economic outcomes

Costs of the installation of the software program and training of the general practice staff to use the software (**Outcome 8**) will be summarised using descriptive statistics.

Health care service costs (**Outcome 9**) will be compared between the intervention and control arms using a GLM with a log link and gamma distribution, two-part model or mixtures model depending on the distribution of costs.

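### Both SAPs specify the between-arm comparison of per-patient health service costs without any provision for clustering by practice or for the stratification factors

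*SAP*

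**What the plan says.** Section 2 (Trial Design) of the CKD SAP sets the design: "The unit of randomisation is the general practice, where practices are randomly allocated concurrently on 1:1 ratio". The cancer-risk SAP has the same design.

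The cost outcome is measured on patients. CKD outcome 11 (section 4.1) is "Cost of primary care service utilisation per patient per year", and cancer-risk outcome 9 (section 4.2) is defined in the same words.

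The analysis is given in one sentence in each SAP. In CKD section 4.6.3 costs "will be compared between the intervention and control arms using a GLM with a log link and gamma distribution, two-part model or mixtures model". Cancer-risk section 4.4.6 repeats this: "using a GLM with a log link and gamma distribution, two-part model or mixtures model depending on the distribution of costs". Neither sentence mentions GEE, a practice random effect, a cluster-robust variance, GP FTE or IRSD terciles.

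Section 3.1 of each SAP sets the inference for effects in general: "Estimates of the intervention effect will be reported with 95% confidence intervals and two sided-p-values".

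**The concern.** Patients of one practice tend to resemble each other, and the arm is assigned to the practice as a whole. A regression that treats such patients as independent overstates the information in the data. Its point estimate of the cost ratio or difference may be sound, but its standard error is too small.

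The gap stands out because the SAPs specify clustering outcome by outcome. The primary outcome is also called a GLM, and there the authors add that the models "use Generalised Estimating Equations with an exchangeable correlation structure and robust standard errors to allow for correlation of outcomes within general practice". The encounter rate (CKD outcome 9, cancer-risk outcome 6), which is the outcome closest to primary care cost, has fixed effects for the stratification factors "and random effect for general practice". Cost has neither.

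At stake is the between-arm cost result of both studies: a chance difference between practices could be reported as an effect of the programme on cost.

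**Working it through.** **1. Is the clustering method given anywhere else?**

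| Main between-arm model | Clustering method | GP FTE and IRSD terciles |
|---|---|---|
| CKD primary, outcomes 1, 2, 6 (4.6.1, 4.6.2) | GEE, exchangeable, robust SE | yes |
| CKD outcomes 3, 4, 5, 8 (4.6.2) | practice random effect | yes |
| CKD outcome 7 (4.6.2) | GEE, exchangeable, robust SE | yes |
| CKD outcome 9 (4.6.2) | practice random effect | yes |
| Cancer-risk primary, outcomes 1 to 5 (4.4.4, 4.4.5) | GEE, exchangeable, robust SE | yes |
| Cancer-risk outcome 6 (4.4.5) | practice random effect | yes |
| Cancer-risk outcome 7, Cox (4.4.5) | robust SE by practice | yes |
| CKD outcome 11, cost (4.6.3) | none stated | none stated |
| Cancer-risk outcome 9, cost (4.4.6) | none stated | none stated |

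Section 3 of each SAP (significance level, multiplicity, adherence) contains no general rule on clustering. The gap is also not one left to the protocol. CKD section 1.1 places the immediate health economic outcomes in the SAP and sends only the longer-term simulation to the protocol. Cancer-risk section 1.1 likewise claims the health economic analyses for the SAP.

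**2. What follows if the model is fitted as written?**

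The SAPs give no ICC for cost and no number of patients per practice (m), so there is no plan figure to reproduce. Both are assumed here, with equal practice sizes. The ICC is to be read as the correlation left after the stratification factors.

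- Design effect: DE = 1 + (m − 1) × ICC
- True SE / unadjusted SE = √DE
- True two-sided type I error at nominal 5% = 2 × [1 − Φ(1.96 / √DE)]

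Worked example, m = 50 and ICC = 0.02: DE = 1 + 49 × 0.02 = 1.98; √DE = 1.41; 1.96 / 1.41 = 1.39; error = 2 × [1 − Φ(1.39)] ≈ 16%.

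| m (assumed) | ICC (assumed) | DE | √DE | True type I error | Coverage of nominal 95% CI |
|---|---|---|---|---|---|
| 25 | 0.01 | 1.24 | 1.11 | 7.8% | 92.2% |
| 50 | 0.02 | 1.98 | 1.41 | 16.4% | 83.6% |
| 50 | 0.05 | 3.45 | 1.86 | 29.1% | 70.9% |
| 100 | 0.05 | 5.95 | 2.44 | 42.2% | 57.8% |

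**3. Does the formula carry over to a gamma model with log link?**

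This was checked by simulation under no arm effect, with 20 practices per arm, a within-practice coefficient of variation of 1 and 400 replicates (all assumed).

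| m | ICC | Formula | Simulated, unadjusted SE | Simulated, SE clustered by practice |
|---|---|---|---|---|
| 50 | 0.01 | 10.8% | 12.5% | 7.0% |
| 50 | 0.02 | 16.4% | 16.8% | 7.0% |
| 50 | 0.05 | 29.1% | 30.5% | 5.3% |
| 100 | 0.01 | 16.5% | 16.0% | 7.5% |
| 100 | 0.02 | 25.6% | 21.0% | 5.5% |
| 100 | 0.05 | 42.2% | 42.3% | 5.5% |

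The simulation noise is about 1 percentage point near 5% (√(0.05 × 0.95 / 400) = 0.011) and about 2 points near 25%. The formula and the simulation agree within about two such units. Clustering the standard errors removes most of the inflation. What remains fits noise together with the known small-sample optimism of robust standard errors with 40 practices.

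**The case against.** The strongest reply is that the SAPs are silent rather than wrong. They name model families and leave the choice to the cost distribution, and they fix no variance estimator. A gamma GLM can be fitted with cluster-robust standard errors without departing from the text. This stands in part: a reader might infer that the authors decided to ignore clustering, and the documents do not say so. But silence is not harmless here. The primary outcome shows that in these SAPs the word GLM does not bring GEE or robust errors with it, since there they are added explicitly. The cost analysis is also assigned to health economists rather than to the biostatistician who runs the other models, so an unwritten assumption is less safe.

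A second reply is that cost is not the only analysis without a stated method. This is correct. The fallback survival models and the competing-risk sensitivity analysis (cancer-risk 4.4.5) and the pattern-mixture models (CKD 4.7.1.3, cancer-risk 4.5.5) name none either. Those are contingent analyses. The contrast holds for the main model of each primary and secondary outcome, and should not be read as covering every planned model.

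A third reply is that little inference is planned for cost. Neither health economic section mentions an interval or p-value, and neither Table 3 has a row for cost. That limits the point but does not remove it: costs are to be compared between arms, and section 3.1 applies 95% intervals and p-values to effect estimates without exception.

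**Conclusion.** The point holds as an omission in the specification, in both SAPs. Fitted as written, the cost comparison would not respect the unit of randomisation, and its intervals and p-values would be too optimistic for any positive ICC. The direction needs no further assumption. The size does: across the assumed values in step 2 the true type I error runs from about 8% to about 42%, and the documents do not say where in that range, or outside it, the trial lies.

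Two stronger readings are tempting and are not supported. One is that cost must be strongly clustered because charges are set by the practice. The SAPs list the charge items but not the level at which they are set, so a large ICC cannot be presumed. The other is that a cost-effectiveness conclusion or the main trial results are compromised. Neither SAP plans a cost-effectiveness ratio, and the primary and secondary outcome models deal with clustering properly. The severity is therefore moderate.

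**What to change.** In CKD section 4.6.3 and cancer-risk section 4.4.6, add a sentence stating that:

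- the cost model is fitted by GEE (gamma, log link, exchangeable correlation, practice as cluster) with robust standard errors, or with a practice random effect;
- if a two-part or mixtures model is chosen, intervals come from a cluster bootstrap that resamples whole practices within arm;
- GP FTE group and IRSD tercile are included as covariates, as for the other outcomes.

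The cost is one sentence in each SAP and no new data. Intervals will usually be wider, although the covariates may recover some precision. If the number of practices is small, robust standard errors may remain slightly optimistic, as the clustered results in step 3 suggest, and the report should say so.

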4.7 Supplementary Analysis

4.7.1.1 Sensitivity analysis 1: Adjustment of additional covariates

Sensitivity analysis of primary and secondary outcomes will additionally adjust for three confounders measured at baseline: prior practice participation in a formalised quality improvement program (yes, no), patient's age at baseline, sex (male, female, other). These variables will be added as covariates to the regression models described for the primary analysis.

4.7.1.2 Sensitivity analysis 2: Intercurrent events

All eligible patients will be included in the primary ITT analysis, including any patients who die during the trial period. Patients who become pregnant during the trial will also be included in the ITT analysis, although treatment is likely to be deferred for these patients by the general practitioner as these medications are not recommended during pregnancy. We expect the numbers who die over the 12 months of the trial period or become pregnant to be less than 10% of the sample size and similar in the two arms. However, if they do exceed 10% of the sample size, we will conduct a sensitivity analysis for the primary outcome excluding these patients from the ITT analysis.

4.7.1.3 Sensitivity analysis 3: Missing outcome data

- 1) A sensitivity analysis will be conducted to assess the robustness of the missing data assumption using a pattern-mixture model for the primary outcome if more than 10% of the eligible patients have missing responses either because of patient and/or practices withdraw from the trial.
- 2) For the secondary outcomes related to pathology test results and observations (outcome 3 to 8), there may be missing data at baseline and/or the end of the trial for various reasons. For instance: (1) the pathology test was not ordered, or blood pressure not measured; (2) pathology test was ordered/blood pressure measured but the results were either incorrectly recorded (e.g., non-sensical beyond physiological belief), or not recorded in the EMR; (3) general practitioners may have recorded a prescription or an observation such as blood pressure, but they might not have been recorded in a field that is extracted by GRHANITE and stored in the Patron dataset; (4) the patient did not attend the practice during the trial period. Given the complexity of the EMR data and different reasons for the missing data, it is difficult to determine at this stage the most appropriate statistical methods to handle the missing data. ^{12,13} The approach will be determined after a blinded review of the missing data patterns, the reason for missing data and their corresponding mechanism, and the SAP will be updated accordingly. The techniques that may be used to handle incomplete data include adding additional covariates associated with missing data to the mixed effects linear model for continuous outcomes, multiple imputation approach and/or using a pattern-mixture model.

4.7.2 Adherence-adjusted analysis

The effects of incomplete adherence on the estimated intervention effects will be investigated using a complier average casual effect (CACE) analysis¹⁴⁻¹⁶ for the primary outcome only. Prior to conducting the data analysis, study investigators and the data management team, masked to the practice's study arm allocation and informed by the process evaluation, will meet to review adherence with the intervention protocol and construct the indicators for incomplete adherence based on the level of FHT QI program integration within each practice. These will be:

 the number of days that the QI module is active within each practice that will take into consideration whether practices experienced technical issues during the trial period, such as delayed initiation of the intervention or the FHT QI program was available for intermittent periods of time during the trial period. We will consider practices to have adhered to the intervention if the FHT QI program was accessible for at least 75% of the time during the 12 months of the trial duration. Other cut-points may be considered after a masked review of the process evaluation measures.

- 2) the number of FTE general practitioners and FTE nurses compared to the number of computers where the FHT QI module is installed/accessible by general practice clinicians as a proxy measure of the degree of access to the point of care clinical decision support tool. FHT QI platform was not installed on all the computers in some general practices. Thus, some general practitioners/nurses within these practices may not have been exposed to the FHT platform or may have had limited access to the platform, specifically the point of care clinical decision support tool. The cut-point for non-adherence will be defined after masked review of the process evaluation measures.
- 3) the degree of engagement of general practices with the different components of the intervention (e.g., ECHO series, use of the FHT tool to create cohorts) which will be informed by the process evaluation.

A separate CACE analysis will be conducted for each of the nominated adherence indicators above. A two-stage least squares instrumental variable regression will be undertaken where the adherence variables are binary indicator variables and study arm used as the instrumental variable for adherence to the intervention. We will use robust estimation for the variance to account for clustering by general practice and adjust for the stratification factors (practice size and IRSD terciles). Sensitivity analyses using other statistical methods for incomplete adherence may also be conducted to assess the robustness of underlying assumptions.¹⁶

4.7.3 Subgroup Analysis

Three sub-group analyses will be conducted, regardless of the trial findings of the primary analyses.

- Patients that had a recommendation to consider initiation of a statin may have been prescribed ACEI/ARB or did not require this class of medications at baseline. Thus, we will conduct a subgroup analysis using the same regression models described above for the secondary outcomes 1, 5 and 6 by whether patients receive a recommendation to consider initiation of ACEIs/ARBs at baseline. For patients that receive a recommendation to consider initiation of ACEIs/ARBs at baseline and receive a prescription for the class of medications during the trial period, we will investigate the effect of the time between receiving their first prescription to the most recent measure of the pathology measure at the end of the trial period (<3 months; >=3-6 months; >=6 months) for the secondary outcomes 5 and 6, as appropriate. These findings may be reported in part with the primary analysis or in a separate publication.
- 2. Patients that had a recommendation to consider initiation of an ACEI/ARB may have been prescribed statins or may not require statins at baseline. Thus, we will conduct a sub-group analysis using the same regression models described above for the secondary outcome 2 and 4 by whether patients would receive a recommendation to consider initiation of statins at baseline. For patients that receive a recommendation to consider initiation of statins and

receive a prescription for statin during the trial period, we will investigate the effect of the time between receiving their first statin prescription to the most recent measure of the pathology measure at the end of the trial period (<3 months; >=3-6 months; >=6 months) for outcome 4, as appropriate. These findings may be reported in part with the primary analysis or in a separate publication.

3. The statistical analyses described for the primary and secondary outcomes will be repeated for eligible patients with and without a recorded diagnosis of type 2 diabetes at baseline. This subgroup analysis will be reported in a separate paper to the primary analysis.

The statistical analysis for each subgroup will be conducted by including the subgroup variable and its interaction with the intervention as fixed effects to the regression models. Summary statistics will be presented for each sub-group within each study arm, as well as estimates for the intervention effects (appropriate to the outcome type) with a 95% confidence interval and a p-value corresponding to the interaction term between the study arm and the subgroup variable. The estimates may also be displayed on a forest plot.

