3.2 Adjustment for multiple tests including description of controlling for type I error

No adjustments will be made for multiplicity. Separate sample sizes were determined for the respective primary outcomes for the CKD and cancer-risk studies and different samples will be drawn from the respective populations for the two studies. The total number of practices recruited in the trial were based on the sample size required for the CKD arm of the trial.

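### CKD subgroup interaction tests for outcomes 3, 4, 5, 8 and 9 assume that the subgroup difference is identical in every practice within an arm, and are too optimistic if it is not

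*SAP*

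**What the plan says.** All references are to the CKD SAP.

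- **Design (section 2).** "The unit of randomisation is the general practice, where practices are randomly allocated concurrently on 1:1 ratio".
- **Outcomes 3, 4, 5 and 8 (4.6.2).** These are systolic pressure, four lipids, uACR and eGFR. They get a linear mixed model in which arm, the baseline measure where appropriate and the stratification factors "will be fitted as fixed effects and general practice as a random effect".
- **Outcome 9 (4.6.2).** Encounter rate gets a Poisson or negative binomial mixed model with "fixed effects for study arm and the randomisation stratification factors (GP FTE and IRSD terciles), and random effect for general practice".
- **Primary outcome and outcomes 1, 2, 6 and 7 (4.6.1, 4.6.2).** These use GEE with an exchangeable correlation and robust standard errors clustered on practice. No small-sample correction is stated.
- **Subgroups (4.7.3).** All three are patient-level: an ACEI/ARB recommendation at baseline (outcomes 1, 5, 6), a statin recommendation (outcomes 2, 4) and diabetes. The last covers every outcome: "The statistical analyses described for the primary and secondary outcomes will be repeated for eligible patients with and without a recorded diagnosis of type 2" (the sentence goes on to name the condition). The closing paragraph then sets one method for every subgroup, "including the subgroup variable and its interaction with the intervention as fixed effects to the regression models", and reports subgroup-specific estimates with 95% intervals and the interaction p-value.
- **Error rate (3.1, 3.2).** "Estimates of the intervention effect will be reported with 95% confidence intervals and two sided-p-values", and "No adjustments will be made for multiplicity".

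For the mixed-model outcomes, neither 4.6.2 nor 4.7.3 mentions a practice-by-subgroup random term or a robust variance.

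**The concern.** Arm is constant within a practice and subgroup membership varies within it. The arm-by-subgroup interaction is therefore a comparison, between two sets of practices, of the within-practice subgroup difference. Its error should include how much that difference varies from practice to practice. A practice random effect, read in its ordinary sense as a random intercept, moves both subgroups by the same amount and drops out of the difference. The interaction is then judged essentially against patient-level error.

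If practices differ in, say, how they manage diabetic relative to other CKD patients, that variation can be reported as a subgroup effect of the program. The SAP gives some reason to expect variation: 3.3 and 4.7.2 describe outages, incomplete installation and uneven engagement between practices, and two of the subgroups are defined by the recommendations that the software delivers.

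Thirteen interaction p-values are exposed: eight for diabetes (systolic pressure, four lipids, uACR, eGFR, encounters), four for the statin recommendation (lipids) and one for the ACEI/ARB recommendation (uACR). The diabetes results are planned as a separate paper.

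**Working it through.** The SAP states no subgroup error rate, so there is no figure to reproduce. From the SAP come the two-sided tests with 95% intervals (read as nominal 5%), 1:1 allocation by practice, one practice random effect, and fixed subgroup terms. Everything else below is assumed.

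**Notation.** m is patients per practice; q is the share in the subgroup; s² is the patient-level variance, 0.95 with total SD 1 and ICC 0.05; tau is the between-practice SD of the subgroup difference, in outcome SDs, remaining after any baseline adjustment.

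**Linear outcomes.**

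- True variance of one practice's subgroup difference: V_true = s²/(m q(1−q)) + tau².
- Variance that the random-intercept model implies, with slope variation absorbed into the residual: V_model = (s² + tau² q(1−q))/(m q(1−q)). Here tau² is in effect divided by m.
- The number of practices cancels from the ratio. Rejection rate with no true interaction = 2(1 − Φ(1.96 √(V_model/V_true))).

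Example with m = 50, q = 0.5, tau = 0.2: m q(1−q) = 12.5. V_true = 0.95/12.5 + 0.04 = 0.116. V_model = (0.95 + 0.01)/12.5 = 0.0768. The ratio is 0.662 and its square root 0.814, so 1.96 × 0.814 = 1.595, which gives 11.1%.

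Over q = 0.3 to 0.5:

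| tau | m = 20 | m = 50 | m = 100 | m = 200 |
|---|---|---|---|---|
| 0 | 5.0% | 5.0% | 5.0% | 5.0% |
| 0.1 | 5.5–5.6% | 6.3–6.5% | 7.6–8.1% | 10.2–11.2% |
| 0.2 | 7.0–7.3% | 10.1–11.1% | 15.2–16.9% | 23.7–26.4% |
| 0.3 | 9.4–10.2% | 16.1–18.0% | 25.2–28.0% | 37.5–40.8% |

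**Simulation check** (40 practices, cluster-size CV 0.6, q = 0.4, 200 replicates per setting, Monte Carlo SE about 1.5 to 2.7 points; some mixed-model fits gave convergence warnings):

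| mean m, tau | as planned | plus random subgroup slope | GEE, robust SE |
|---|---|---|---|
| 50, 0 | 5.0% | 4.5% | 5.5% |
| 50, 0.1 | 7.0% | 5.0% | 6.0% |
| 50, 0.2 | 12% | 6.5% | 7.0% |
| 100, 0.1 | 7.5% | 5.0% | 6.5% |
| 100, 0.2 | 18% | 6.0% | 9.0% |

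**With a baseline covariate.** A further small simulation that adjusted for baseline gave about 5% with no slope variation. At a slope SD of 0.2 it gave about 14% (mean 40 patients) and 20% (mean 80). Practice-clustered robust variance with a t reference on practices minus 2 df stayed near 4–7%.

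**Outcome 9, formula only.** On the log-rate scale v = (1/mu + alpha)(1/(mq) + 1/(m(1−q))), and the rejection rate is 2(1 − Φ(1.96/√((v + tau²)/v))). Take mu = 8 encounters, m = 50, q = 0.4, so the second bracket is 1/20 + 1/30 = 0.0833.

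- For pure Poisson, v = 0.125 × 0.0833 = 0.0104. With tau = 0.1 the variance ratio is 1.96, and 1.96/1.4 = 1.4 gives 16.2%.
- Negative binomial dispersion 0.4 gives 7.7%, and 0.8 gives 6.5%.
- With tau = 0.2 the three rates are 37.3%, 15.7% and 11.2%.

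These figures are for the interaction test. The subgroup-specific intervals rest on the same assumption but were not quantified separately.

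**The case against.** The best case for leaving the text alone has four parts.

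1. **The fault is conditional.** A reader might infer that subgroup claims from these models would carry an error above 5%. The SAP does not support that. With no variation in the subgroup difference the planned test holds its 5%, and nothing in the document says how much variation there is. This stands.
2. **The larger figures may not apply.** The SAP gives no cluster size. The cohort is restricted to CKD patients who may benefit from drug treatment (2.1), and missing results are expected for outcomes 3 to 8 (4.7.1.3), so analysable numbers per practice may be modest. Baseline adjustment may also absorb part of any lasting practice difference, which leaves a smaller residual tau. This stands as a caution on size. It does not remove the problem, because inflation persisted with a baseline covariate when residual slope variation was present, and 4.6.2 lists no baseline covariate for outcome 9.
3. **The other outcomes are not a clean benchmark.** A reader might infer that the same subgroup question is tested validly under GEE and invalidly here. That is too strong. GEE with robust standard errors allows for the variation, but without a small-sample correction it rejected at 5.5 to 9.0% in simulation. Using GEE for binary and ordinal outcomes and mixed models for the rest is a coherent choice, not a contradiction.
4. **The stakes are low.** These are supplementary analyses. Thirteen unadjusted tests, if independent, already give 1 − 0.95^13 = 49% for at least one false positive. This is true and limits the priority, but it is no reason to let each test exceed its nominal level as well.

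**Conclusion.** The point holds in conditional form. For outcomes 3, 4, 5, 8 and 9 the subgroup tests and intervals in 4.7.3 need the subgroup difference to be constant across practices within an arm. If it is not, they are too optimistic, increasingly so with more patients per practice. For the linear outcomes the illustrative size is about 5 to 6.5% where variation or practices are small, and about 10 to 25% for 50 to 200 patients per practice with a residual slope SD of 0.2 outcome SDs. Practice numbers, cluster sizes, ICC and slope variance are all assumptions, so no single figure can be assigned to this trial. A reader might also infer that the trial's main conclusions are at risk; they are not, because the primary and main secondary analyses contain no such interaction. This is a cheap improvement.

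**What to change.** Add one sentence to CKD SAP 4.7.3: for outcomes 3, 4, 5, 8 and 9, the interaction test and the subgroup-specific intervals come from a model that also has a practice-level random coefficient for the subgroup variable. If that model does not converge, keep the random-intercept model and use practice-clustered robust standard errors with a t reference based on the number of practices (for example, practices minus 2).

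The order matters. In simulation the random coefficient gave 4.5 to 6.5%, and the robust t option about 4 to 7% in the check with a baseline covariate. The fallback is in line with the robust variance already planned for the primary outcome and outcomes 1, 2, 6 and 7.

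The cost is one sentence, one extra model option and somewhat wider intervals for the subgroup contrasts. No new data are needed.
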